- 1) To prospectively examine the psychosocial outcomes of women with sporadic breast cancer who have CPM versus those who do not. We will also determine the impact of patient and physician characteristics on the outcomes. We hypothesize that women who have CPM will have more decisional regret (the primary outcome), cancer-specific distress, cancer worry, and fear of recurrence and lower satisfaction with their decision than those who do not have CPM.

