Study Measures. The domains chosen for study measures are based on the Integrated Model of Behavior^{45,46} and Ottawa Decision Framework⁴⁷ as well as results of our R21 study of decision-making and CPM.

Background Information. Participant will complete demographic information (i.e., age, race, ethnicity, marital status, education, and occupation). Medical variables (i.e., date of breast cancer diagnosis, method of detection, tumor histology, nuclear grade, stage, human epidermal growth factor receptor (HER2/neu), estrogen receptor (ER) and progesterone receptor (PR) status, and weight and height at diagnosis) will be extracted from patients' charts.

Cancer-Specific Distress. Cancer-specific distress will be measured with the Revised Impact of Events Scale (IES). The IES assesses two common categories of responses to stressful events: intrusion and avoidance. The IES has good internal consistency reliability (0.70 to 0.85).⁴⁸ For this study, patients will be asked to rate the frequency of intrusive thoughts and avoidance behaviors related to their cancer.^{48,49}

Breast Cancer Worry Scale. Breast cancer worry will be assessed with a 4-item scale developed by Lerman et al.^{49,50} These items assess the extent to which worry about breast cancer interferes with women's daily functioning.

Fear of Cancer Recurrence. Fear of recurrence will be assessed with a 5-item scale that measures patients' beliefs and anxieties about disease recurrence.^{51,52} It has been used with a variety of cancer populations and the psychometric properties of this measure have been well-established.^{53,54}

Satisfaction with Decision Scale. A measure of women's satisfaction with their surgery decision.⁵⁵ It has been used with a variety of healthcare decisions

and has been shown to have good reliability and validity.⁵⁵ It will be administered at 1, 6, 12 and 18 months post-surgery.

Decisional Regret. This brief scale measures distress or remorse about the surgical decision.⁵⁶ It has been used to assess regret with a variety of healthcare decisions and has been shown to be reliable and valid.⁵⁶ It will be administered at 1,6,12 and 18 month assessments.

4.0 Statistical Considerations.

Analytic Methods:

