General: Our first steps will be to summarize patients' baseline demographic, risk behavior, and disease-related information using descriptive statistics. This will include means, standard deviations, medians and ranges for continuous variables and frequencies and percentages for categorical responses. Descriptive statistics will be summarized separately for each group and for each group over time for psychosocial variables.

Groups of women will include women who have had CPM and those who have not had CPM. For women for whom we have information on their initial interest in CPM, the latter category of women also being categorized by those who initially had an interest in CPM versus those who did not have an interest in CPM. We will compare information about these groups of women for continuous variables using t-tests, analyses of variance (or their nonparametric equivalents such as Wilcoxon rank sum tests) or for categorical variables chi-square tests or Fisher's Exact tests. Group comparisons tested for significance will include the two primary groups of CPM versus no CPM and also for the women for whom we have information on their initial interest in CPM, the three following groups: initial interest and had CPM, initial interest but did not have CPM, and no interest and did not have CPM.

Our initial primary analyses for each psychosocial variable will evaluate women's psychosocial outcomes over time using a general linear model (PROC GLM in Statistical Analysis Software (SAS)) incorporating information over time (baseline and 1, 6, 12, and 18 months post-surgery) with the psychosocial variable being the dependent variable and whether or not the women had CPM the independent variable. We will determine if the psychosocial variable (on average) differs between the groups, if there are differences over time (averaged over groups), and whether or not these differences of time are different for different groups (a group by time interaction). Analyses will be made in SAS version 9.3 (SAS Institute Inc., Cary, NC, USA).

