Missing Data. Because we are using patient-reported outcomes, some individuals will fail to complete all questionnaires. PROC GLM in SAS is designed to handle this type of missing data and will give unbiased estimates of effects over time provided that the probability of having missing data depends only on the covariates in the model. We will check this assumption by looking at predictors of missing data. We will also run analyses to examine whether study participants who drop out of the study early differ from those who do not. With the use of PROC GLM, we will be able to include all participants in the analysis, even those with missing values for some time points and those who drop out early. We will also use alternative multiple imputation methods to estimate missing values using differing assumptions if the data appear to not be missing at random. Several

strategies will be used to decrease the chance of missing data and non-compliance. Forms will be reviewed upon receipt to ensure all items are completed, and if incomplete, participants will be contacted to determine if the question was deliberately skipped and, if not, to get a response. Patients will be contacted numerous times by mail and by phone to ensure questionnaire completion. Scheduling of follow-up visits will coincide with clinic visits, and as such, missing data will be kept at a minimum.

Sample size: Given information from the recently completed R21 study and rates over the past 5 years, we estimate that approximately 11.5% of women meeting eligibility criteria will have CPM. All power analyses assume a significance level of 0.05 and a two-sided test. Assuming a 10% attrition rate and an additional loss of 10% of patients due to eligibility changes post-enrollment, we will enroll approximately 345 participants to ensure that approximately 311 participants continue on study to yield complete data on at least 280 participants. Therefore, about 32 women will have CPM, and 248 will not. For comparisons of these two groups of women, a sample size of 280 (32 in the CPM group and 248 in the non CPM group) at 18 months post-surgery will provide 80% power to detect an effect size of 0.54 or greater for the continuous dependent variables.

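### Does the plan leave open which decisional-regret comparison decides the hypothesis?

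*Combined protocol and SAP*

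**What the plan says.** The specific aim in section 1.0 hypothesises that women who have CPM will report "more decisional regret (the primary outcome), cancer-specific distress, cancer worry, and fear of recurrence and lower satisfaction with their decision". Regret alone carries the primary label. Section 3.0, Study Measures, says of the regret scale: "It will be administered at 1,6,12 and 18 month assessments". Baseline is not among its visits.

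Section 4.0, Analytic Methods (General), opens the longitudinal analysis with "Our initial primary analyses for each psychosocial variable will evaluate" and uses one model per scale, with CPM status as the independent variable. It asks "if the psychosocial variable (on average) differs between the groups, if there are differences over time (averaged over groups") and then "whether or not these differences of time are different for different groups (a group by time interaction"). On who is compared, it states: "Group comparisons tested for significance will include the two primary groups of CPM versus no CPM". A three-group split by initial interest in CPM is added for women with that information.

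Under Sample size in section 4.0, "All power analyses assume a significance level of 0.05 and a two-sided test". The text first powers a two-group comparison at 18 months (32 versus 248 women, effect size 0.54, 80% power). It then powers a group effect across visits in a linear mixed model, assuming no interaction with time (32 versus 227 women). That second paragraph refers to primary psychosocial outcomes in the plural.

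**The concern.** One primary outcome does not make one primary test. For regret, three contrasts could bear on the group hypothesis: the difference averaged over visits, the difference at 18 months, and the group-by-time interaction. No sentence says which one decides. The plural in the sample-size text can also be read as promoting the other scales to primary status.

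If the contrast were picked after the data were seen, the nominal 5% error would not hold. If the averaged and 18-month results disagreed, the plan would not say which one answers the question. The study is meant to inform women about an irreversible operation, so this looks worth settling beforehand.

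**Working it through.** **Inputs.** From section 4.0: two-sided 0.05; 32 versus 248 women at 18 months; effect size 0.54; within-woman correlation r = 0.3, 0.5, 0.7. From section 3.0: four regret visits. Assumed here: equal SD at each visit, the same correlation between all visits, complete data.

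**1. The plan's own figure.** The standard error of a difference in SD units is sqrt(1/32 + 1/248) = 0.188. Then 0.54/0.188 = 2.875, and 2.875 − 1.960 = 0.915, which gives power 0.820 (0.817 by noncentral t). The stated 80% is reproduced. The difference detectable at exactly 80% is (1.960 + 0.842) × 0.188 = 0.526 SD (0.528 by t).

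**2. How far the two group contrasts overlap.** A four-visit mean has variance (1 + 3r)/4. The correlation between the 18-month and averaged estimates is sqrt((1 + 3r)/4) = 0.689, 0.791, 0.880 for r = 0.3, 0.5, 0.7.

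**3. Error if either could be claimed.** With two standard normal statistics so correlated and no true difference:

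| r | either significant, two-sided | either significant, more regret after CPM |
|---|---|---|
| 0.3 | 8.4% | 4.2% |
| 0.5 | 7.9% | 3.9% |
| 0.7 | 7.2% | 3.6% |

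The references are 5% and 2.5%. The two-sided excess is 2.2 to 3.4 percentage points.

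**4. Whether one contrast is clearly better.** Power with 32 versus 248 women, by noncentral t:

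| True difference | 18 months | Average, r = 0.3 / 0.5 / 0.7 |
|---|---|---|
| 0.54 SD at every visit | 82% | 99% / 95% / 90% |
| 0.03, 0.18, 0.36, 0.54 SD at 1, 6, 12, 18 months (mean 1.11/4 = 0.2775) | 82% | 57% / 46% / 39% |

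The second row is an illustration; the plan predicts no such late pattern. Neither contrast is better in both cases.

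**5. What the text supports.**
- *Average difference.* The hypothesis is that one group has more regret, with no time course. The General paragraph lists the average group difference first. The mixed-model paragraph powers that effect and assumes no interaction.
- *18 months.* This appears only in a power statement. The longitudinal analysis does not list it as a test, although the general provision for t-tests would allow one.
- *Interaction.* An overall group-by-time test asks whether the patterns over time differ. A significant result does not by itself show more regret in the CPM group, so it is not a natural route to confirming the hypothesis.
- *Time effect averaged over groups.* This says nothing about CPM.
- *Baseline.* The model is described for five visits, but regret is collected at four, so for regret the average can only run over 1, 6, 12 and 18 months.
- *Plural outcomes.* In the General paragraph, primary describes the analyses. In the sample-size text the plural sits in a visibly garbled parenthesis, against an explicit singular in section 1.0.

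**The case for a change.** The strongest case for a change is that order of listing is not designation. The 18-month comparison is powered first, and the averaged effect as described includes a baseline that regret does not have. The model also differs between paragraphs: the missing-data text says "With the use of PROC GLM, we will be able to include all participants in the analysis", while the sample-size text uses a mixed model. One sentence would settle the matter at no cost in patients, and it works only if written before analysis.

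Part of this stands. No sentence designates the contrast, and the plural is loose. But the error rates in step 3 show what silence would permit, not what the plan provides for; nothing in it says that any significant contrast suffices. CPM is chosen, not randomised, so fixing one contrast would not by itself make the result a dependable guide to the decision. The choice of SAS procedure, and the detectable differences in Table 3, are separate questions. Neither shows that the regret hypothesis lacks a natural test.

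**Conclusion.** The concern describes missing detail, not an error. The primary outcome, the two groups compared and the significance level are fixed. The hypothesis, the first-listed test and the mixed-model power paragraph all point to the CPM versus no-CPM difference in regret averaged over the post-surgical visits. An analyst would fill the gap that way and report the 18-month and interaction results beside it. The singular/plural mismatch is a slip of wording.

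The exposure, if either the averaged or the 18-month contrast were claimed, is a two-sided error of 7.2% to 8.4% instead of 5%. This rests on equal correlation across four visits, complete data and an either-counts rule that the plan does not state. Preferring 18 months would be a fair trade-off: it gives up 8 to 17 points of power for a constant 0.54 SD difference (82% against 90% to 99%) and gains 25 to 43 points for the illustrated late difference (82% against 39% to 57%). That is the sponsor's judgement. No change to the plan is called for.

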2.0 BACKGROUND AND RATIONALE

Breast cancer is the leading cause of cancer among women in the U.S., affecting approximately 226,870 women annually.¹⁴ The majority of patients (93%) are diagnosed with operable disease and undergo surgical management of the affected breast with either breast conserving surgery or mastectomy.¹⁵ It is well recognized that adjuvant systemic chemotherapy has substantially reduced the probability of dying from breast cancer.¹⁶ Among women with hormone-positive breast cancers, adjuvant treatment with tamoxifen or aromatase inhibitors reduces the risk of developing a contralateral breast cancer by

approximately 50%.⁹ In fact, it is estimated that the combination of mammography screening and adjuvant systemic therapies have contributed to a 30% overall reduction in breast cancer mortality over the past decade.¹⁷

Despite these major achievements over the past two decades in reducing breast cancer mortality through evidence-based practices, there has been a rising incidence of CPM. The combined annual rate of CPM (~8%) in population-based studies of women with invasive breast cancer or ductal carcinoma in situ^{2,3} translates into over 18,000 potentially over-treated patients based on an expected 226,870 new breast cancer cases in 2013.¹⁴ Rates of CPM are even higher in academic medical centers and were estimated to be between 14-28% from 2006 to 2007.¹⁸⁻²⁰ These higher than average annual rates of CPM at centers that offer multidisciplinary care may reflect an increasing trend in the numbers of patients with sporadic breast cancer electing to undergo CPM and the availability of plastic surgery expertise for reconstruction. Our previous studies with breast cancer patients suggest that, before meeting with their surgeon, 59% of women indicated they had at least some interest in CPM. Hawley et al. reported in a population-based survey of women from Detroit and Los Angeles that among women undergoing a mastectomy of their affected breast, 53% said that they considered CPM.²¹ Thus, the topic of this proposal affects the majority of women with stage I-III breast cancer.

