Since the primary psychosocial outcomes (such as decisional regret distress and scale) include repeated measurements that are correlated within subjects, our approach will utilize linear mixed model analysis (LMM, a special case of generalized linear mixed modeling in which each outcome variable is continuous). For the LMM analyses of continuous dependent variables across time (baseline, 1, 6, 12, and 18 months post-surgery), we calculated detectable effects based on a wide range of homogeneous correlations, namely, 0.3, 0.5, and 0.7, between repeated measurements. To simplify the power calculation procedure, we assume that there is no interaction between treatment and time points. The detectable effects of treatment are presented in Table 3. The calculations were done using PASS 2005 (Power Analysis and Sample Size Software). We provide a brief explanation of the results presented in the first row. In the first row, the homogeneous correlation between treatments across time points is assumed to be 0.3. A sample size of 259 (32 in the CPM group and 227 in the non CPM group) will provide 80% power to detect a standard deviation (SD) in means across groups of 0.10 (an effect size of 0.19), which corresponds to the means of 0, 0.290 (in SD unit) in the two groups. The above figure provides the power plot by effect size on treatment when the correlations (r) are 0.3, 0.5, and 0.7, respectively.

[figure not shown]

Table 3. Detectable treatment effects over time using LMM analysis with 80% power

Correlation between assessment (r)	Detectable mean diffs effects on treatment	SD of effect on treatment	Effect Size among treatment
0.3	0, 0.290	0.10	0.19
0.5	0, 0.306	0.11	0.19
0.7	0, 0.340	0.12	0.19

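### The pooled-variance primary analysis (PROC GLM) is sensitive to unequal SDs at about 32 versus 248 women, and the plan makes no provision for them

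*Combined protocol and SAP*

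**What the plan says.** All of this is in section 4.0, Statistical Considerations, unless noted.

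- Under General, simple group comparisons are made "for continuous variables using t-tests, analyses of variance (or their nonparametric equivalents such as Wilcoxon rank sum tests"). The plan does not say whether the t-test is the pooled or the unequal-variance form.
- One set of comparisons is CPM versus no CPM. Another, only for women whose initial interest is known, has three groups: "initial interest and had CPM, initial interest but did not have CPM, and no interest and did not have CPM".
- The initial primary analyses are run "using a general linear model (PROC GLM in Statistical Analysis Software (SAS)) incorporating information over time", with CPM status as the independent variable. They test group, time, and "whether or not these differences of time are different for different groups (a group by time interaction").
- Under Sample size, "about 32 women will have CPM, and 248 will not", and these numbers at 18 months "will provide 80% power to detect an effect size of 0.54 or greater for the continuous dependent variables".
- The later power text says that "our approach will utilize linear mixed model analysis" for the repeated outcomes. It does not say whether the residual covariance may differ by group, and it does not reconcile this model with PROC GLM.
- Descriptive statistics, including SDs, will be given by group and over time, but no rule says what follows if the SDs differ.

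Decisional regret, the primary outcome (section 1.0), is measured at four post-surgery assessments (section 3.0, Study Measures).

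**The concern.** A pooled analysis estimates one error variance from all women. Here the non-CPM group supplies nearly all of that estimate, while the small CPM group supplies nearly all of the uncertainty in the mean difference. If CPM scores are more variable than non-CPM scores, the standard error is too small, intervals are too narrow and the test rejects too often. If they are less variable, the test is conservative.

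The direction cannot be known beforehand. At stake is the error rate of the CPM comparison and of the group-by-time test for every psychosocial outcome, including decisional regret. If the method is chosen only after the group SDs have been seen, the choice is no longer prespecified.

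**Working it through.** **Inputs.** From the sample-size text: n1 = 32 (CPM), n2 = 248 (no CPM), two-sided 5%, effect size 0.54, power 80%. The document gives no SD for either group, so the SD ratio s (CPM divided by non-CPM) is an assumption, varied from 0.67 to 1.5.

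**The plan's own figure.** With a common SD, the noncentrality is 0.54 / √(1/32 + 1/248) = 0.54 / 0.1878 = 2.875. The normal approximation gives power Φ(2.875 − 1.96) = 0.820. The pooled t-test (278 df) gives 0.817 and the Welch t-test (about 39 df) gives 0.801. The stated 80% is reproduced. The effect detectable with 80% power is 0.528 for the pooled test and 0.539 for Welch; the plan does not name the test behind 0.54.

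**Why the imbalance matters.** The CPM group's weight in the pooled variance is 31/278 = 11%. At equal SDs its share of the variance of the mean difference is (1/32) / (1/32 + 1/248) = 89%.

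**Group comparison.** With the non-CPM SD set to 1:

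- pooled variance = (31s² + 247) / 278
- assumed SE² = pooled variance × (1/32 + 1/248)
- true SE² = s²/32 + 1/248
- k = assumed SE / true SE, and true size ≈ 2·P(Z > 1.96k)

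Example, s = 1.25: pooled variance = (48.44 + 247)/278 = 1.063; assumed SE² = 1.063 × 0.03528 = 0.0375; true SE² = 0.04883 + 0.00403 = 0.0529; k = √(0.0375/0.0529) = 0.842; size = 2·P(Z > 1.65) = 9.9%.

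**Group-by-time test.** Take four complete assessments, compound symmetry with correlation 0.5, and the same s at every visit. Each of the three within-woman contrasts then has the same variance ratio k², so size ≈ P(χ² with 3 df > 7.815k²). At s = 1.25 this is P(χ² > 7.815 × 0.709 = 5.54) = 13.6%.

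| s | k | Group, formula | Group, simulated | Group-by-time, formula | Group-by-time, simulated |
|---|---|---|---|---|---|
| 0.67 | 1.354 | 0.8% | 0.8% | 0.25% | 0.24% |
| 0.8 | 1.187 | 2.0% | 2.0% | 1.2% | 1.1% |
| 1 | 1 | 5.0% | 5.1% | 5.0% | 5.3% |
| 1.1 | 0.929 | 6.9% | 6.8% | 8.0% | 8.0% |
| 1.25 | 0.842 | 9.9% | 9.9% | 13.6% | 13.8% |
| 1.5 | 0.735 | 15.0% | 15.0% | 23.8% | 23.8% |

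The simulations used normal scores with 200,000 replicates (group) and 20,000 (group-by-time). Independent repeats of the lowest group-by-time entry gave 0.3%.

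**Is the imbalance the cause?** At 140 versus 140 the pooled size stays at 4.9% to 5.1% for every ratio from 0.5 to 2. With the 32 versus 227 split used in the mixed-model power text, the result is almost unchanged (14.6% at s = 1.5).

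**Do the alternatives hold their level?** For normal scores the Welch t-test has size 4.9% to 5.2%. A compound-symmetry covariance fitted by group has 4.7% to 5.4% for both longitudinal tests. A mixed model with one covariance for both groups has the same sizes as the pooled analysis on complete data. The Wilcoxon test does not remove the problem: 1.9%, 7.3% and 8.8% at s = 0.67, 1.25 and 1.5.

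**Where Welch is worse.** With exponential (strongly right-skewed) scores and equal SDs, Welch has size 6.5% against 4.9% for the pooled test. The excess is lopsided: 0.9% for a falsely higher CPM mean and 5.6% for a falsely lower one. A permutation test on the Welch statistic has 4.3% to 5.8% for exponential scores over s = 0.67 to 1.5.

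**The case against.** The strongest reply is that no defect has been shown. The document gives no group SDs, at equal SDs the pooled analysis is correct, and the larger figures need a ratio of 1.5; at 1.1 the group comparison has a size of only 6.9%. That stands, and it limits the point to an improvement. A reader might infer that the planned tests are inflated; the document supports neither that nor the opposite.

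A reader might also infer that the 80% power at 0.54 holds only at equal SDs. That does not follow. Once the SDs differ, the unit of the effect size is undefined. With 0.54 in non-CPM SD units, Welch power runs from 97.6% at ratio 0.67 to 48.6% at 1.5. In CPM SD units it runs from 75.2% to 82.3%. All that can be said is that the 0.54 figure assumes a common SD.

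Nor can the three-group comparison be given a size. It covers only women whose initial interest is known, and its group numbers are not stated. Deriving them from the statement in section 2.0, about the sponsor's previous studies, that "59% of women indicated they had at least some interest in CPM" would stack several assumptions.

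Two further replies are partly right. The t-test may already be the Welch form, and the mixed model could carry group-specific variances. Both are open rather than wrong, but neither alters PROC GLM as named. The nonparametric option is attached only to the simple comparisons. Finally, the longitudinal sizes assume complete data, while the plan expects some missing questionnaires, so they are illustrative.

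**Conclusion.** The point holds as a gap in the plan, not as a demonstrated error. The analysis named as initially primary pools its error variance or covariance across groups of about 32 and 248, and the plan provides for no other case. If the CPM SD were 1.25 times the non-CPM SD, a nominal 5% group comparison would run at about 10% and the group-by-time test at about 14%. If it were 0.67 times, they would run at about 0.8% and 0.3%. These figures rest on assumed ratios and normal scores. Those for the group-by-time test rest also on complete data, compound symmetry and one ratio at all visits. The importance is minor to moderate: the sensitivity is certain, its actual size is unknown, and the remedy is cheap.

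**What to change.** Prespecify one primary longitudinal method in section 4.0: the linear mixed model already described there, in place of the pooled PROC GLM. Give it a parsimonious residual covariance that differs by group (for example compound symmetry by group, two extra parameters) and Satterthwaite or Kenward-Roger degrees of freedom. Changing the procedure alone does not remove the pooling; the group-specific covariance does.

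For the simple comparisons, name the Welch (Satterthwaite) t-test for CPM versus no CPM and Welch's ANOVA for the three groups. Report a permutation analysis of the Welch statistic as a sensitivity analysis only, and state that the prespecified primary method governs if the two disagree. Add a sentence saying that the 0.54 figure assumes a common SD.

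The cost is a few sentences, with no change to enrolment or data collection. If SDs are equal and scores normal, Welch loses about 1.6 points of power at 0.54 (81.7% to 80.1%), so the stated 80% is still met. If SDs are equal and scores strongly right-skewed, Welch brings mild, lopsided inflation (about 6.5% against 4.9%), which is why the permutation analysis is reported.

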
3.0 RESEARCH DESIGN AND PROCEDURES

Study Population. Patients will include women seen at MDACC (n=245) or K-S (n=100) who meet the following inclusion criteria: ductal carcinoma in situ (DCIS) or Stage I-III newly diagnosed sporadic unilateral invasive breast cancer; over age 18; and able to speak, read, and write in English. Patients with previous breast cancer, prior history of prophylactic mastectomy or are known to have a germline gene mutation that predisposes them to an increased risk of breast cancer (e.g., BRCA1, BRCA2), and/or if they are considered at high risk for contralateral breast cancer on the basis of a strong family history of cancer will be excluded.⁴⁴ Based on our estimates over the past 5 years and the data from our completed R21 study, we expect that at least 10-15% of women who come for surgical treatment for ductal carcinoma in situ (DCIS) or Stage I-III unilateral breast

cancer will opt for CPM. Thus, for patients approached at their initial surgical consult appointment, we will screen all eligible patients during the 27-month recruitment period for initial interest in CPM (see section below) at the time of recruitment to identify women who are and who are not initially considering CPM. Spouse/partner eligibility: married or living with partner for at least 1 year, 18 years or older, able to speak, read and write in English.

Study Procedures.

After completing the initial set of questions (patient information/demographics questions for all patients and screening questions for patients seen at initial surgical consult), patients who consent to the study will be given questionnaires to complete at five time points: baseline (around the time of study enrollment), and approximately 1, 6, 12, and 18 months following their surgery for breast cancer. For participants who prefer to complete the study survey(s) electronically, participants may complete on-line versions of the same survey(s) using REDCap (Research Electronic Data Capture).

Participants will receive a \$20 gift card after completing the study questionnaire at each time point to compensate them for their time and effort. They can receive up to \$100 in gift cards if they complete questionnaires at all 5 time points. Parking reimbursement will be provided for patients and spouses participating in the optional interview if he/she opts for an in-person interview at MD Anderson.

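### The average group effect counts the enrolment baseline as an outcome visit, which dilutes a post-surgery difference in distress, worry and fear of recurrence; the five-visit model and power basis also do not fit regret and satisfaction, which have four visits

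*Combined protocol and SAP*

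**What the plan says.** Section 3.0 (Study Procedures) schedules questionnaires at "baseline (around the time of study enrollment), and approximately 1, 6, 12, and 18 months following their surgery for breast cancer". Section 3.0 (Study Measures) restricts two scales to the post-surgery visits. For satisfaction with decision: "It will be administered at 1, 6, 12 and 18 months post-surgery". For decisional regret: "It will be administered at 1,6,12 and 18 month assessments". No separate schedule is given for distress, worry or fear of recurrence.

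Section 4.0 (General) applies one primary model to each psychosocial variable, "incorporating information over time (baseline and 1, 6, 12, and 18 months post-surgery"), with "whether or not the women had CPM the independent variable". The first test is described as "We will determine if the psychosocial variable (on average) differs between the groups". A time effect and a group-by-time interaction are also tested. The baseline score is nowhere named as a covariate, and the repeated-measures model has no contrast confined to the post-surgery visits.

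Section 4.0 (Sample size) gives two power statements. One is a single-visit comparison of 32 and 248 women: "at 18 months post-surgery will provide 80% power to detect an effect size of 0.54 or greater for the continuous dependent variables". The other is a linear mixed model over five visits including baseline, with 32 and 227 women. It names decisional regret among its outcomes and, as a stated simplification, assumes no treatment-by-time interaction. Table 3 gives detectable differences of 0.290, 0.306 and 0.340 SD at correlations 0.3, 0.5 and 0.7.

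**The concern.** A measurement taken before surgery cannot carry an effect of surgery. If it is averaged in with the later visits, the group effect mixes the pre-existing gap between self-selected groups with whatever arises afterwards. With only about 32 women expected to have CPM, lost power is costly.

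The power assumption compounds this. No interaction over five visits means the same group difference at every visit, including baseline. A difference that begins at surgery is itself a group-by-time interaction, so the mixed-model power statement describes a difference already present at enrolment.

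For the primary outcome the problem is different and simpler: regret has no baseline score, so the five-visit model cannot be fitted to it as written.

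**Working it through.** **Inputs.** Two-sided 0.05 and 80% power; group sizes 32 and 248 (18 months) and 32 and 227 (mixed model); homogeneous correlation r = 0.3, 0.5, 0.7. All are from section 4.0 (Sample size). The multiplier is 1.960 + 0.842 = 2.802.

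**1. The plan's own figures.**
- 18-month comparison: √(1/32 + 1/248) = 0.1878, and 2.802 × 0.1878 = 0.526 SD. At the stated 0.54 SD, power is 82%. This reproduces.
- Table 3: with m visits the variance factor of a subject's mean is (1 + (m−1)r)/m. With √(1/32 + 1/227) = 0.1888, the detectable difference is 2.802 × 0.1888 × √factor. Values are in SD units:

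| r | factor, 5 visits | factor, 4 visits | detectable, 5 visits | detectable, 4 visits | Table 3 |
|---|---|---|---|---|---|
| 0.3 | 0.440 | 0.475 | 0.351 | 0.365 | 0.290 |
| 0.5 | 0.600 | 0.625 | 0.410 | 0.418 | 0.306 |
| 0.7 | 0.760 | 0.775 | 0.461 | 0.466 | 0.340 |

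Table 3 does not reproduce with either visit count. At its stated differences, power is 64%, 55% and 54% with five visits, and 61%, 54% and 53% with four. The PASS settings are not given. Nothing below relies on Table 3's values.

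**2. What the average estimates.** With complete data and compound symmetry, the average group effect is the difference in five-visit means: (B + 4D)/5 = 0.8D + 0.2B. For B/D = −0.5, 0, 0.5 and 1 the ratio to D is 0.70, 0.80, 0.90 and 1.00. Simulation with D = 0.5 and r = 0.5 gave 0.796 at B = 0 (theory 0.80) and 0.921 at B = 0.3 (theory 0.92).

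**3. Cost when the groups start equal (B = 0).** Take D with 80% power on the four-visit mean: 0.365, 0.418 and 0.466 SD. On the five-visit mean the standardised effect is 0.8 × 2.802 × √(four-visit factor / five-visit factor) = 2.33, 2.29 and 2.26. Power is **64%, 63% and 62%**. Put the other way, 80% power on the five-visit average needs D = 0.351/0.8, 0.410/0.8 and 0.461/0.8 = 0.439, 0.512 and 0.576 SD.

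**4. What the planned interaction test recovers.** At the same D, the 4-df group-by-time test has noncentrality 0.8D²/(0.1888²(1−r)) and power 34%, 59% and 92%. If either test may succeed, each at 0.025 (an illustrative split; the plan states none), power is 65%, 75% and 93%.

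**5. Regret and satisfaction.** No baseline enters, so step 2 does not apply. Moving from five to four visits multiplies the detectable difference by √(four-visit factor / five-visit factor) = 1.039, 1.021 and 1.010.

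**6. Would adding the baseline score as a covariate settle it?** Suppose a baseline gap b and no CPM effect. If the gap persists, the bias is b unadjusted, b(1−r) with the covariate and 0 for change from baseline. If it fades completely, the bias is 0, −br and −b. For an assumed b = 0.3 SD that fades (32 and 248 women), the covariate analysis rejects 12%, 26% and 55% of the time, against 5% for the unadjusted four-visit mean. The documents give no gap size.

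**The case against.** The strongest reply is that the same section already plans a group-by-time test, which is the natural test for a difference that appears only after surgery. This stands in part. At r = 0.7 that test alone exceeds the 80% reference; at r = 0.3 it does little. It also gives no single post-surgery estimate to report.

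It can also be said that the primary outcome is barely touched. That stands. A reader might infer that the regret analysis is biased or shrunk by a fifth. It is not, because regret has no baseline score. Nor is the enrolment target undermined: 345 × 0.9 × 0.9 ≈ 280, and the 18-month comparison built on those 280 women needs no baseline.

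The main inference can be questioned. The plan does not say scale by scale that distress, worry and fear of recurrence are collected at baseline, nor that baseline always precedes surgery. The phrase "for patients approached at their initial surgical consult appointment" implies that some women are approached at another time, which is not specified. Both inferences are the natural reading of the schedule, but they remain inferences.

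The covariate list is also not presented as closed: these are called initial analyses, and the aim includes patient and physician characteristics. Even so, the baseline score is given no role other than as a response.

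**Conclusion.** The plan needs correcting on this point, at moderate weight. For three of the five hypothesised outcomes the average group effect is 0.8D + 0.2B. If the groups start equal, a difference with 80% power on the post-surgery visits drops to about 62% to 64% on that test, partly offset by the interaction test.

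This rests on a pre-surgery baseline for those three scales, complete data, a constant post-surgery difference and homogeneous correlation. A reader might infer a general 20% shrinkage. The documents do not support that, because women choose their surgery and B need not be zero. A reader might also infer that baseline adjustment should lead the analysis. Step 6 shows that this is a trade-off in self-selected groups.

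For regret and satisfaction the five-visit model and power basis are a specification error without bias, and the visit count is worth 1% to 4%. That small figure does not describe the change from the published table: the four-visit formula values are 26%, 37% and 37% above Table 3, because Table 3 itself does not reproduce.

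**What to change.** - Define the CPM effect in the repeated-measures model as the group difference averaged over the 1, 6, 12 and 18-month visits, with the 18-month contrast alongside. This can be a post-surgery contrast with baseline kept as a response, or a model of the four visits only.
- For distress, worry and fear of recurrence, report baseline-adjusted and change-from-baseline estimates as supporting analyses, and state what each assumes about a baseline gap.
- State which scales are collected at baseline. Flag any baseline questionnaire completed after surgery and repeat the analysis without it.
- State four visits for regret and satisfaction, and restate the mixed-model power on that basis: 0.365, 0.418 and 0.466 SD under the standard formula with 32 and 227 women. Document the PASS settings behind Table 3, or correct the table.

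The cost is analysis wording and a short power restatement. No new questionnaire is needed. The flag needs completion and surgery dates. The baseline-adjusted analysis needs a rule for missing baseline scores, for which the multiple imputation already mentioned under Missing Data could serve. The visible consequence is that the stated detectable differences become larger.
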